5.2 Exclusion criteria

Commercially Confidential Information

2. Significant illness which has not resolved within two (2) weeks prior to initial dosing.

Commercially Confidential Information

Commercially Confidential Information

Commercially Confidential Information

19. Pregnant or nursing (lactating) women at screening.
20. Sexually active males, at screening, baseline and during the study, unwilling to use a condom during intercourse while taking investigational drug

Commercially Confidential Information

21. Women of child-bearing potential, defined as all women physiologically capable of becoming pregnant, at screening.

Commercially Confidential Information

22. Use of other investigational drugs within 5 half-lives of Screening, or within 30 days of dosing, whichever is longer; or longer if required by local regulations

Commercially Confidential Information

6 Treatment

6.1 Study treatment

Details on the requirements for storage and management of study treatment, and instructions to be followed for subject numbering, prescribing/dispensing and taking study treatment are outlined in the SOM and/or Pharmacy Manual.

Refer to the ‘dietary restrictions and smoking’ [Section 6.2.3.1](#) for subjects’ restrictions.

6.1.1 Investigational and control drugs

The investigational drug, KAE609 and the matching placebo will be prepared by Novartis and supplied as open labeled bulk medication to the unblinded site pharmacist ([Table 6-1](#)). An unblinded pharmacist or authorized designee is required to dispense the study drug. Drug will be administered at the clinical site by the study personnel in accordance with the specified study procedures.

Table 6-1 Investigational and control drug

Investigational/ Control Drug (Name and Strength)	Pharmaceutical Dosage Form	Route of Administration		Sponsor (global or local)
KAE609 15mg/mL (2 mL vial)	Solution for Injection	Intravenous use	Open label bulk supply; vials	Sponsor global
Matching Placebo	Solution for Injection	Intravenous use	Open label bulk supply; vials	Sponsor global

6.1.2 Additional study treatments

No additional treatment beyond investigational drug and control drug are included in this trial.

6.1.3 Treatment arms/group

All dose levels are provisional with the exception of cohort A1 in Part A (SAD).

Commercially Confidential Information

Commercially Confidential Information

6.2 Other treatment(s)

6.2.1 Concomitant therapy

All medications, procedures and significant non-drug therapies (including physical therapy and blood transfusions) administered after the subject was enrolled into the study must be recorded in the concomitant medications / significant non-drug therapies or procedures Case Report Forms from screening through the post study safety follow-up call. For further details on potential drug-drug interactions, see Investigator's Brochure.

6.2.2 Prohibited medication

Except for any medication which may be required to treat adverse events, no medication (including vitamins or herbal remedy) other than study treatment will be allowed from the date subject signs the informed consent until the post study safety follow-up call. In case of prior use of concomitant medication with long half-life additional time might be needed (e.g. less than 5 half-life between drug intake and screening or pharmacodynamic effect has not returned to normal). For further details on potential drug-drug interactions, see Investigator's Brochure.

Should a subject have an incidental and limited need for a medication to be taken within the restricted pre-dose timeframe (e.g. paracetamol/acetaminophen for a headache, etc.), the sponsor should be advised, as administration of any concomitant medication *may* require the subject to be withdrawn.

6.2.3 Restriction for study subjects

For the duration of the study, the subjects should be informed and reminded of the restrictions outlined in this section.

6.2.3.1 Dietary restrictions and smoking

Commercially Confidential Information

Commercially Confidential Information

6.2.3.2 Other restrictions

Commercially Confidential Information

6.3 Subject numbering, treatment assignment, randomization

6.3.1 Subject numbering

The subject number assigned to a subject at screening remains the unique identifier for the subject throughout the study. For information on subject numbering, please see ‘Subject numbering’ section in the SOM.

6.3.2 Treatment assignment, randomization

The randomization numbers will be generated using the following procedure to ensure that treatment assignment is unbiased and concealed from subjects and investigator staff. A randomization list will be produced by or under the responsibility of Novartis Global Clinical Supply (GCS) using a validated system that automates the random assignment of treatment arms to randomization numbers in the specified ratio.

The randomization scheme for subjects will be reviewed and approved by a member of the Randomization Office.

If only single investigational site, then randomization will be in a sequential fashion using the randomization schedule. Randomization should only occur when all baseline data has been reviewed and eligibility is confirmed.

Follow the details outlined in the SOM regarding the process and timing of treatment assignment and randomization of subjects.

6.4 Treatment blinding

This is a subject and investigator-blinded study. Subjects will remain blinded to study treatment throughout the study, except where indicated below.

The identity of the treatments will be concealed by the use of study drugs that are all identical in packaging, labeling, schedule of administration, appearance, and odor.

Site staff

With the exception of any unblinded site staff identified below, all site staff (including study investigator and study nurse) will be blinded to study treatment during treatment allocation and subject dosing.

Unblinding a single subject at site for safety reasons (necessary for subject management) will occur via an emergency system in place at the site.

Commercially Confidential Information

Drug product will be supplied in bulk, so an unblinded pharmacist who is independent of the study team will be required in order to maintain the blind. This unblinded pharmacist will receive a randomization list or treatment allocation cards from GCS with the appropriate treatment allocation numbers. Appropriate measures must be taken by the unblinded pharmacist to ensure that the treatment assignments are concealed from the rest of the site staff.

Trained site staff will be required to administer study treatment. Appropriate measures must be taken by the unblinded site staff to ensure that the treatment assignments are concealed from the rest of the site staff.

Sponsor staff or delegate

The following unblinded sponsor roles are required for this study:

- Unblinded field monitor(s)
- Unblinded clinical staff managing drug re-supply to site
- Unblinded sample analyst(s) (PK)

The unblinded field monitors are required to review drug accountability and allocation at site. The unblinded monitors are not provided with a randomization list directly but will be unblinded through review of source documentation compiled by the unblinded pharmacist, which details treatment allocation to individual subjects. The unblinded monitors will also be able to review the treatment allocation cards/randomization list provided to the unblinded pharmacist. The names of the unblinded monitor(s) are detailed in the monitoring plan.

The sample analysts will receive a copy of the randomization schedule (via request to the Randomization Office), to facilitate analysis of the samples. The sample analysts will provide the sample data to the study team under blinded conditions unless otherwise allowed.

The study statistician will be able to access the full randomization list from the start of the study and is allowed to share unblinded information with the rest of the clinical trial team as appropriate for internal decision purposes, as outlined in [Table 6-2](#). For example, unblinded summaries and unblinded individual data can be shared with the team whenever necessary.

The study statistician is also allowed to share treatment assignments with the investigator during dose escalation meetings CCI when knowledge of the treatment assignments could aid decision-making.

Study programmers and other personnel involved in study data analysis CCI are allowed to access treatment assignment information from the start of the study for the purpose of data analysis.

The clinical trial team is allowed to share unblinded results with other sponsor staff (e.g. decision boards) as required for internal decision making on the study or the project while the study is ongoing.

All unblinded personnel will otherwise keep randomization lists and data or information that could unblind other study team members confidential and secure except as described above.

Following final database lock all roles may be considered unblinded.

Table 6-2 Blinding levels

Role	Time or Event			
	Randomization list generated	Treatment allocation & dosing	Safety event (single subject unblinded)	CCI dose escalation
Subjects/Patients	B	B	UI	B
Site staff	B	B	UI	B
Unblinded site staff (see text for details)	B	UI	UI	UI
Drug Supply and Randomization Office	UI	UI	UI	UI
Unblinded sponsor staff (see text for details)	B	UI	UI	UI
Statistician/statistical programmer/data analysts	UI	UI	UI	UI
All other sponsor staff not identified above	B	B	UI	UI

B Remains blinded

UI Allowed to be unblinded on individual patient level

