4.1 Rationale for study design

This is the first clinical study for KAE609 administered iv with the purpose of establishing safety, tolerability and pharmacokinetics in healthy subjects. The rationale for key design elements in this study include:

- **Healthy subjects:** Enrolling healthy subjects was chosen to reduce the risk of introducing confounding variables and to minimize the risk and severity of adverse events. This minimizes any underlying disease-related findings that may confound data interpretation that may exist, especially regarding transaminase elevations, which have been seen in patients with uncomplicated malaria treated with KAE609 and can be present in patients with severe malaria.
- **Randomization:** Helps to avoid possible bias in the selection and allocation of subjects.
- **Placebo comparator:** Use of a placebo helps assess if any safety or tolerability findings should be attributed to KAE609 and helps to maintain study blinding.
- **Blinding:** Blinding of subjects with limited un-blinding of investigators and sponsor minimizes bias in the conduct of the study. The Sponsor's clinical trial team will be blinded. Representatives of the Sponsor, such as the Translational Medicine Expert, may be only unblinded to facilitate safety-related decisions. Limited un-blinding of the investigators and sponsor (e.g., at the time of dose-escalation review) will be allowed if needed to help with safety-related decisions. The pharmacist at the CRO who prepares the injections will be unblinded.
- **Sequential cohorts:** This allows for an adequate safety and tolerability assessment prior to the initiation of each ascending dose.
- **Sentinel dosing:** No sentinel dosing is planned for this study. The predicted toxicities are monitorable and reversible. There is no expected effect on QT and no CNS toxicities expected in this study. A QT potential risk was seen in the hERG assay but no effect of oral KAE609 on QTcF has been observed in healthy subject or patient studies so far. Sentinel dosing is not likely to reduce the risk in this study.
- **Domiciliation:** Subjects will be domiciled before and during dosing and after last dosing to allow for close observation of safety and tolerability, and to ensure compliance with instructions for all subjects.

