9.1.4 Study stopping rules

Cohort stopping rules and dose escalation decision points:

Dose escalation, as well as continued dosing within any given cohort, will be paused and may be stopped based on full review of all available clinical safety data and discussion with the Investigator if any of the following occur:

- Any treatment-emergent SAEs, except those that are clearly and incontrovertibly due to extraneous causes
- Two or more subjects in the same cohort experience a similar AE which was assessed as CTCAE grade 3 or greater in intensity, and are considered as potentially related to the study treatment;
- The Sponsor considers that the number and/or severity of AEs, abnormal safety monitoring tests or abnormal laboratory findings justify putting the study on hold
- Two or more subjects experience Grade 2 or higher hypersensitivity reactions
- Two or more subjects experience Grade 3 or higher injection site reactions.
- Two or more subjects with QTcF greater than 500 msec and/or an increase greater than 60 msec, expected to be related to the study treatment

The severity of adverse events will be graded by the study site investigator (or sub-investigator) based on CTCAE and captured in the CRF (see [Section 10.1](#)). This information will be used to quantify events that may lead to subject's discontinuation or stopping dose escalation.

Drug administration of subsequent cohorts will only be triggered if an adequate safety and tolerability profile has been confirmed from the preceding cohort.

Safety reviews will be conducted jointly between medically qualified representatives of the Sponsor and Investigator and a joint decision will be made. If a dose level is identified to be intolerable, the preceding dose level will be defined as the maximum tolerated dose.

Overall study stopping rules:

Enrollment in the study will be placed on hold and dosing held if any of the rules for a cohort or dose escalation are met as above.

The study may resume following the safety review, if the investigator and Sponsor agree it is safe to proceed.

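### Protocol 4.1 and the 6.4 text allow the investigator to learn treatment assignments at dose-escalation meetings, Table 6-2 does not, and no visible rule fixes adverse event ratings first

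*Protocol*

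**What the plan says.** The study is presented throughout as subject- and investigator-blinded. Three places govern what the investigator may know at dose escalation.

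- **Protocol 4.1 (Blinding):** "Limited un-blinding of the investigators and sponsor (e.g., at the time of dose-escalation review) will be allowed if needed to help with safety-related decisions".
- **Protocol 6.4, text:** "The study statistician is also allowed to share treatment assignments with the investigator during dose escalation meetings", when that knowledge might assist the decision. The same section says that, apart from the unblinded staff it identifies, "all site staff (including study investigator and study nurse) will be blinded to study treatment during treatment allocation and subject dosing".
- **Protocol 6.4, Table 6-2:** the row reads "Site staff B B UI B". The last column is dose escalation and B means still blinded. The other code, UI, means "Allowed to be unblinded on individual patient level". At dose escalation UI is given to a separate row for unblinded site staff, but not to ordinary site staff.

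On rating, Protocol 9.1.4 says: "The severity of adverse events will be graded by the study site investigator" or a sub-investigator. Section 10.1.1 makes relationship to study treatment part of each adverse event record. Section 10.1.3 relies on the investigator's suspicion of causality for late serious events. The SAP says nothing about who may know assignments at escalation, or about the order of rating and unblinding.

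**The concern.** A site that follows the table would keep the investigator blinded at an escalation meeting. A site that follows the text could hand over the assignments. Both would be compliant with some part of section 6.4.

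The inconsistency matters because of who is involved. Adverse events are a primary endpoint (12.4.1). Their severity and relatedness are tabulated by treatment (Protocol 12.4.2, SAP 7.2). Protocol 4.3 gives, as one reason for having placebo, a better judgement of whether events are due to the drug. A relatedness rating made with the assignment known cannot serve that purpose. The same ratings feed the pausing rules in 9.1.4.

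**Working it through.** No power, error rate or sample-size figure is at issue, so the check is to set the passages side by side.

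**1. Is it the same person?** Yes. The site-staff sentence in 6.4 names the study investigator as included. The unblinded site roles visible in 6.4 are the pharmacist and, by implication, staff giving the drug; the investigator is not among them. The investigator therefore falls in the ordinary site-staff row of Table 6-2.

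**2. Is it the same event?** Yes, as far as the visible text shows. The 6.4 sentence refers to dose-escalation meetings and the table column is headed dose escalation. Redaction sits next to both and may conceal a further event, but it does not remove this one.

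**3. Is it the same rule?** No.

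| Source | Investigator at dose escalation | Condition |
|---|---|---|
| 4.1 | Limited unblinding allowed | Needed for a safety-related decision |
| 6.4 text | Assignments may be shared | Knowledge might assist the decision |
| Table 6-2 | Remains blinded | None stated |

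The two narrative sections agree on direction but differ on threshold. The table differs from both. The site-staff sentence in 6.4 does not settle it, because it covers only allocation and dosing.

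**4. Can ratings be made after sharing?** Section 3 places the review after each cohort is complete and before the next is dosed. The visible text does not define complete. Three routes remain:

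- Adverse event monitoring continues for at least 30 days after the last dose (10.1.1), whereas the end-of-study visit is Day 8 in Part A and Day 12 in Part B. Events can be open or newly reported after a review.
- Section 10.1.1 requires changes in severity to be reassessed at each visit, so a recorded rating can be revised.
- Section 9.1.4 pauses dosing within a cohort for review. The investigator takes part in safety reviews and in the joint decision. If assignments are shared there, subjects of that cohort may still be under treatment and observation.

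**5. Where would it show?** In the tables of maximum severity and of related events, and in the pausing rules that use grade or relatedness. One such rule is met when at least two subjects of a cohort have a similar event of grade 3 or more judged potentially related. With a count of two, a single rating can decide whether it is met.

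**6. Is there a visible safeguard?** Not for this route. The emergency code break (6.6.3) requires date, time and reason to be noted and the monitor to be told at once. Nothing comparable is visible for sharing at escalation meetings.

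**The case against.** The strongest reply is that this unblinding is deliberate and disclosed. Section 4.1 allows it, the 6.4 text repeats it, and escalation is a joint safety decision in which knowing assignments can help. On that view the table cell is the outlier and correcting it is enough. Much of this stands. It is why the direction of the reconciliation should be left to the sponsor, and why a reader who infers that the investigator must be denied assignments goes too far. It does not remove the conflicting cell, the two thresholds, or the absence of a visible rule on rating first.

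Other stronger readings also lack support:

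- **Sponsor team.** Section 4.1 says the "clinical trial team will be blinded" and 6.4 says "unblinded summaries and unblinded individual data can be shared with the team whenever necessary". A reader might infer a second contradiction. But 4.1 goes on to allow limited sponsor unblinding for safety decisions, 6.4 ties sharing to Table 6-2, and the table codes other sponsor staff as UI at dose escalation. What remains is loose wording, since those staff are coded B during allocation and dosing.
- **Carry-over.** A reader might infer that one cohort's assignments reveal the next cohort's. Each cohort is newly randomized with allocation concealed, so any influence is indirect.
- **Size of bias.** Pooled placebo is 5 × 2 = 10 in Part A and 6 (2 × 3) in Part B, so one re-rated subject moves a placebo percentage by 1/10 = 10 points or 1/6 = 16.7 points. That is only the granularity of small groups. It says nothing about how often ratings would change.
- **Whole primary endpoint.** Adverse event incidence by organ class and term does not use severity or relatedness. Vital signs and laboratory values are measured, and Holter QTcF is read by a core laboratory. The primary window also closes at Day 8 or Day 12 (12.4.1), so if a cohort is complete only at that visit, most events in the window will have been collected before the review.

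Finally, a safeguard may exist in redacted text, including 6.5, or in the site operations manual. Its absence from the protocol cannot be asserted, only its absence from the visible text.

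**Conclusion.** The inconsistency holds: 4.1 and the 6.4 text permit what Table 6-2 rules out for the investigator at dose escalation, and the two permissive passages use different thresholds. The consequence is limited. Some severity and relatedness ratings could be made or revised with assignment known: those for events open, changed or first reported after a review, and those made during a within-cohort pause review. The effect falls mainly on the severity and relatedness tables and on the pausing rules that use them. Its size cannot be estimated, because the documents do not say how often assignments would be shared or ratings changed.

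This rests on three assumptions: that the investigator is not among the unblinded staff in any redacted text, that the person attending the meeting is also the rater or a sub-investigator's supervisor, and that no ordering rule sits in material not seen. It does not show that the trial fails to be investigator-blinded, or that unblinding at these meetings is wrong. It is worth correcting because the remedy is cheap and protects the comparison for which placebo was included.

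**What to change.** 1. Reconcile 4.1, the 6.4 text and Table 6-2 so that they state one rule and one threshold for who may be unblinded at dose escalation. Whether the text is narrowed or the table changed is the sponsor's choice.
2. In either case, require that severity and causality for all adverse events to date in that cohort are recorded before any assignment is shared with the investigator at an escalation meeting.
3. Make later changes to those ratings identifiable as made after unblinding.
4. Log each sharing: date, cohort, recipient and reason.

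Emergency code break and urgent safety unblinding are untouched; the recording step applies to sharing at escalation meetings. The cost is protocol wording, a short data-entry step before the meeting and a log. No change to sample size or assessments is needed.

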6.5 Dose escalation and dose modification

For Part A (SAD) and Part B (MAD), safety data reviews will be performed after each dose level in order to decide about the progression to the next dose.

Commercially Confidential Information

Commercially Confidential Information

6.5.1.1 Starting dose

Commercially Confidential Information Please see
[Section 4.2](#) for rationale of dose selection and the pharmacy manual for additional details on
the syringes to be used.

6.5.1.2 Provisional dose levels

[Table 6-3](#) describes the starting dose and the dose levels that may be evaluated during this trial.

Commercially Confidential Information

6.6 Additional treatment guidance

6.6.1 Treatment compliance

In this study subjects will be dosed at the investigator's center by qualified members of the site staff. Details of each dose of study drug will be recorded in the CRF.

PK parameters (measures of treatment exposure) will be determined in all subjects treated with KAE609, as detailed in the [Section 8.5.1](#).

